Non-serious Adverse Event: any other adverse event that does not meet criteria for a serious adverse event.

Definitions of bleeding events are based on the PLATO Trial protocol²⁸, a previously published study comparing Brilinta/ticagrelor to clopidogrel.

- **Major Life-Threatening Bleeding** includes:
 - Any Fatal Bleed
 - Intracranial Hemorrhage
 - Intrapericardial bleed with cardiac tamponade
 - Bleeding resulting in hypovolemic shock or severe hypotension that requires pressors or surgery
 - Clinically overt or apparent bleeding associated with decrease in hemoglobin >5 g/dL
 - Bleeding requiring transfusion of ≥4 U whole blood or PRBCs
- **Other Major Bleeding** includes:
 - Bleed causing clinically significant disability (e.g., intraocular bleed with permanent vision loss)

- Clinically overt or apparent bleeding associated with decrease in hemoglobin >3 g/dL, but < 5 g/dL
 - Bleeding requiring transfusion of ≥ 2 , but < 4 U whole blood or PRBCs
- **Minor Bleeding** includes any bleeding requiring medical intervention but not meeting the criteria for major bleeding

Working Study Definitions:

- **Migraine Headache Day:** any study day in which headache symptoms occur. If a single headache lasts from the end of a calendar day into the beginning of the next, it would be considered a single headache day provided the event lasted less than 24 hours. If headache symptoms last more than 24 hours, it would be considered 2 Headache Days; more than 48 hours would be considered to be three days, etc. Aura alone ("Acephalic migraine") will not be considered a headache. The subject must experience headache pain.
- **"Responder" to Therapy:** $\geq 50\%$ reduction in the average number of monthly headache days during the month of therapy compared with participant's own baseline.
- **"Non-responder" to Therapy:** $< 50\%$ reduction in the number of monthly headache days during the month of therapy compared with participant's own baseline.
- **Platelet Inhibition:** This is a functional definition based on Platelet Reactivity. PRU Test Result (VerifyNow PRU Test, Accumetrics Inc. San Diego CA) of < 140 , while on therapy, will be considered a "positive" inhibitory effect of the medication. PRU results of $141 - 160$ will be considered a borderline response. PRU results > 161 will be considered a negative response.

Primary Study Endpoints:

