- Primary Efficacy Endpoint: A subject will be considered to have achieved the primary efficacy endpoint (a "Responder") if she/he has $\geq 50\%$ reduction in the number of monthly headache days during the month of therapy compared with participant's own baseline. If there is $< 50\%$ reduction in the number of migraine days, she/he will be considered a Non-Responder.
- Primary Safety Endpoint: Major bleeding episode (as defined above) or other life-threatening adverse event (see below), while taking the Brilinta/ticagrelor.

Secondary Study Endpoints:

- Secondary Efficacy Endpoints will be assessed as follows:
 - Absolute reduction in headache days as a continuous response variable.
 - Absolute reduction in headache intensity as a continuous response variable.

- Quantitative comparison of the number of monthly uses of rescue medications in the roll-in versus the treatment phase
- Comparison of time to headache resolution after rescue medications. If < 2 hours to resolution, will be considered a “successful” intervention. Will compare the percentage of successful interventions in the baseline and treatment phases.
- Secondary Safety endpoints: Non-life threatening adverse events to Brilinta/ticagrelor, including:
 - Minor bleeding
 - Allergic reactions
 - Shortness of Breath
 - Rash
 - Extreme fatigue
 - Any other symptom requiring the participant to withdraw from the study prior to completion of the one month medication administration

Subject Recruitment, Eligibility and Screening:

Study subjects will be recruited from hospital-based cardiology and headache clinic at Columbia University Medical Center, and through the private offices of the study physicians.

Preliminary Inclusion Criteria:

- Subject age 18 – 65 years
- Symptoms meet International Headache Society Criteria for Episodic Migraine or Chronic Migraine
- At least one year history of Episodic or Chronic migraine headache symptoms
- At least 6 headache days per month
- Subject agrees to use two forms of birth control or abstinence throughout duration of the study
- Subject able to complete online daily headache log
- Right to left shunt >grade 1 as determined by Transcranial Doppler evaluation

Preliminary Exclusion Criteria:

- Inability to understand the study or history of non-compliance with medical advice
- Currently taking a P2Y12 inhibitor
- Known hypersensitivity to Brilinta/ticagrelor
- History of stroke/transient ischemic attack (TIA) in the previous 6 months

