Baseline-Monitoring Phase (Phase 1): The subject will track her/his headaches daily for 28 days through an online survey tool (REDCap, licensed through Columbia University), to establish a baseline headache frequency. Each day, the subject will receive a text message/e-mail reminder to complete the daily headache log. The message will contain a link to log into the survey tool. During this phase, subjects will answer questions including presence or absence of headache symptoms, severity of headache symptoms, duration of symptoms, impact on daily activities, and use of rescue medication. Any headache lasting more than 24 hours will be counted as a second headache day. After 28 days of monitoring, the study coordinator will assess the subject's data to make sure the subject meets criteria for minimum headache days, and has been consistently performing the daily log. If the number of headache days is insufficient, the subject's participation will be completed. If the subject logs at least 6 headache days in the month, she/he will continue in the study. If the participant has been assigned to the Episodic arm of the study, but has >14 headache days in the screening month, or if the participant has been assigned to the Chronic arm of the study, but has <15 headache days in the screening month, she/he will NOT be reassigned, but will remain in the assigned group for analysis. The subject will then be treated with Brilinta/ticagrelor for a 28-35 day test period (Phase 2). The length of the test period will depend on the timing of the participant's follow-up visit after beginning treatment. The protocol window is 28+7 days.

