Treatment Phase (Phase 2): The subject will return for a follow-up visit to receive her/his medication within 1 week of completing the 28 day headache log. A loading dose of Brilinta/ticagrelor 180 mg will be administered in the office. Thereafter, for 28-35 days, a Brilinta/ticagrelor 90 mg tablet will be taken once in the morning and once in the evening, as close to 12 hours apart as possible. Each day, the subject will receive a text message reminder to login to the website, to record her/his headache activity. If she/he fails to login for two consecutive days, the study coordinator will place a follow-up phone call. PRU testing will be done a minimum of 7 days after the initiation of treatment, but before the medication is completed. A follow-up visit will be arranged between day 28 and day 35 days of monitoring to review efficacy, compliance, and side effects, to return unused medication, and to allow continued access to Brilinta/ticagrelor if indicated. A second Quality of Life survey will be completed.

Continued Access Phase (Phase 3): If the subject has a beneficial response to the Brilinta/ticagrelor (> 50% reduction in the average number of monthly headache days compared with the baseline), she/he will be offered continued access to the medication to complete an additional 2 months of therapy with on-going headache monitoring. A final office visit and Quality of Life Survey will be completed within 7 days of the 56th day of Phase 3 for return of unused medication, empty medication bottles and discussion about future therapeutic options. If the subject fails to have a beneficial response following the first month of treatment (Phase 2), the medication will be discontinued and participation in the study will be completed. If the subject elects to discontinue the Brilinta/ticagrelor, despite a beneficial response, participation in the study will be completed.

Outcomes Assessment/Statistical Analysis

Information from this study will be assessed to determine the feasibility of performing a larger randomized, blinded, placebo-controlled multi-center trial. We will assess not only our therapeutic drug response rate in order to estimate a required sample size for the future trial, but also our ability to recruit patients from local referring sources to estimate the time frame of such a trial. Subject compliance rate with use of daily online questionnaires will be determined. Drop-out rates, related to medication side effects will also be assessed.

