1. Statistical Considerations and Analysis Plan:

This is a prospective, open label single-armed trial designed to evaluate the safety and efficacy of Brilinta/ticagrelor (90 mg twice daily) used off-label, in a young healthy population, for the treatment refractory migraine headache. The primary endpoints are:

- Efficacy – Response to treatment defined as a $\geq 50\%$ reduction in chronic headache during a three month period of therapy, compared with baseline.
- Safety – Bleeding events and adverse medication reactions measured over the 3 month treatment period.

Only 40 subjects will be treated in this initial feasibility trial, 20 with episodic migraine, 20 with chronic migraine. We will assess the number of “Responders” in each study group. Responsiveness will be compared with the measured PRU while on therapy. The results of this trial will be descriptive only. It is not anticipated that the number of subjects enrolled will provide statistically analyzable results.

However, if treatment were to be seemingly beneficial, these data could form the foundation for the development of a pivotal randomized, blinded, prospective trial in a larger cohort as mentioned above.

The safety analysis set will include all subjects who receive at least one dose of study medication. This will be the primary analysis set for all safety endpoints which will include major bleeding complications, and adverse drug reactions. Bleeding outcomes, in this younger, healthier cohort will be compared with the previously published PLATO Trial²¹.

Any participant who completes her/his daily headache logs for at least two weeks, but not the full month of the study period, will be classified according to her/his current response status (LOCF), regardless of whether or not he/she completed the required therapy.

2. Analysis of Secondary Endpoints

The secondary endpoints, which will be reported, are as follows:

- Absolute reduction in headache days as a continuous response variable.
- Comparison of the use of rescue medications in the roll-in versus the treatment phase and “successful” interruption of MHA (< 2 hours to resolution) with rescue therapy.
- Non-major bleeding side effects of the medication

STUDY PROCEDURES:

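### The analysis plan sets the primary efficacy endpoint over three months, the endpoint section sets it over one, and subjects who leave after month 1 have no three-month value

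*Combined protocol and SAP*

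**What the plan says.** Working Study Definitions makes a subject a responder on a 50% or greater "reduction in the average number of monthly headache days during the month of therapy", against the subject's own baseline. Primary Study Endpoints repeats this as the primary efficacy endpoint: a "reduction in the number of monthly headache days during the month of therapy compared with" the subject's baseline.

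The only analysis plan (Outcomes Assessment/Statistical Analysis, item 1) lists the primary efficacy endpoint as a 50% or greater "reduction in chronic headache during a three month period of therapy, compared with baseline". The same item then counts responders in each study group and adds "Responsiveness will be compared with the measured PRU while on therapy"; that blood test is done during Phase 2. Its LOCF rule is for subjects with at least two weeks of logs who miss part of the month, and Withdrawal of Subjects ties the same rule to four weeks.

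Continued Access Phase (Phase 3) decides who has data after month 1: "If the subject fails to have a beneficial response following the first month of treatment (Phase 2), the medication will be discontinued" and participation ends. For the others, "If the subject elects to discontinue the Brilinta/ticagrelor, despite a beneficial response, participation in the study will be completed".

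The introduction to the analysis section gives the purpose of the result: the "therapeutic drug response rate in order to estimate a required sample size for the future trial".

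**The concern.** Two current sections define the primary efficacy endpoint differently. One uses headache days over one month. The other uses an undefined quantity, chronic headache, over three months, although half of the 40 planned subjects have episodic migraine.

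The three-month version also has a structural gap. Entry to months 2 and 3 depends on the month-1 outcome, so many subjects will have no three-month value by design. No rule says how they count. A rate among those with three-month data would be selected on the outcome itself. In an open-label study, two definitions also leave room to choose after the data are seen. What is at stake is the one efficacy figure that is to size the next trial.

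The safety endpoint has a smaller mismatch of the same kind. Primary Study Endpoints limits it to major bleeding or other life-threatening events. The analysis plan's bullet takes in bleeding and adverse drug reactions generally, over three months. Minor or non-major bleeding is secondary in both places.

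**Working it through.** The documents give no alpha, power or expected response rate for this endpoint, so there is no planned figure to reproduce. The check is a comparison of texts, followed by illustrations of size.

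**1. The texts side by side**

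| Place | Measure or rule | Window |
|---|---|---|
| Working Study Definitions; Primary Study Endpoints | Headache days | One month |
| Analysis plan, efficacy bullet | Chronic headache (undefined) | Three months |
| Analysis plan, count per group | Responder, a term defined over one month | One month |
| Analysis plan, PRU comparison | Test taken in Phase 2 | Phase 2 |
| Analysis plan and Withdrawal of Subjects, LOCF | At least two weeks of logs | One month or four weeks |

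The three-month bullet is the outlier.

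**2. Who has a three-month value**

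Planned logging on drug is 28 to 35 days for those who stop after Phase 2. For those who continue it is 28 + 56 = 84 to 35 + 63 = 98 days. With month-1 response *p* and share of responders continuing *c* (both assumed), subjects without a three-month value = 40 − 40*pc*:

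- *c* = 1 and *p* = 0.3, 0.5, 0.7: 28, 20 and 12 subjects.
- *c* = 0.8, counts rounded: 30, 24 and 18 subjects.

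A subject who completes month 1 and then leaves does not trigger LOCF, and no other section assigns a status.

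**3. Simple count**

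Assume *p* = 0.5, *c* = 0.8 and 80% of continuers still responding. There are 20 responders, 16 continuers and 13 still responding (16 × 0.8 = 12.8, rounded).

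- One month: 20/40 = 50.0%
- Three months, leavers as failures: 13/40 = 32.5%
- Three months, leavers keep month-1 status: (13 + 4)/40 = 42.5%
- Three months, continuers only: 13/16 = 81.25%

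One subject can change status. Baseline 10 days, then 4, 6 and 7, is 1 − 4/10 = 60% at one month but 1 − (17/3)/10 = 43% over three.

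**4. Simulation**

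There were 400,000 subjects per cohort and setting. Assumptions:

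- True baseline uniform on 6–14 (episodic) or 15–26 (chronic) days per 28, with at least 6 logged days and independent binomial days.
- Half of subjects have a 70% true reduction and half 10%, with no elective stopping.
- Continuation if the month-1 reduction exceeds 50%.
- Three-month response if the three-month average is at most 50% of baseline.
- All treated subjects in the denominator.

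| True reduction in the better half | Cohort | One month | Leavers fail | Leavers keep status |
|---|---|---|---|---|
| 70% (base case) | Episodic | 49.4% | 41.6% | 45.9% |
| | Chronic | 47.9% | 46.3% | 47.5% |
| 50% | Episodic | 34.3% | 20.9% | 26.8% |
| | Chronic | 27.4% | 17.9% | 21.6% |
| 80% | Episodic | 53.5% | 47.9% | 50.7% |
| | Chronic | 49.9% | 49.5% | 49.7% |

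In the base case, one month minus leavers-fail is 7.8 points (7.8% × 20 = 1.6 subjects) in the episodic cohort and 1.6 points (0.3 of 20) in the chronic cohort. Over the 50% to 80% range it runs from 13.4 to 5.6 points (episodic) and 9.5 to 0.4 points (chronic).

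With 10% or 25% elective stopping, the leavers-fail rate is 37.5% or 31.3% (episodic) and 41.7% or 34.8% (chronic). Continuers only, a denominator that the plan does not state, gives 92.2% in the episodic cohort (73.5% at a 50% true reduction).

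**5. What makes up the base-case gap**

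Response needs at least 50%, while the continuation wording used here needs more than 50%. Subjects at exactly 50% in month 1 are 4.3% (episodic) and 1.2% (chronic). The rest of the gap is 7.8 − 4.3 = 3.5 points and 1.6 − 1.2 = 0.4 points.

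**6. Why scaling is needed**

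Baseline is 28 days and Phase 2 is 28 to 35. An unscaled 35-day count reaches a 50% fall only if the daily rate falls by 1 − 0.5 × 28/35 = 60%. If everyone logs 35 days, the base-case one-month rate is 41.0% raw against 47.7% scaled (episodic) and 42.4% against 48.0% (chronic).

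**The case against.** The strongest reply is that the intended endpoint is plain. Nearly everything outside the bullet fits one month, including the term responder and the LOCF rule in the same item. On that reading everyone who completes Phase 2 has a value, and the missing three-month status arises only if a stray line governs. This stands as far as it goes: it shows which definition to keep. It does not remove a contrary primary endpoint from the only analysis plan.

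Second, results are declared descriptive, and no test, error rate or power is affected. That is true and limits the harm. The response rate still feeds the next trial's sample size.

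Third, the illustrated gap is partly not a matter of window. More than half of the base-case gap comes from subjects at exactly 50% (step 5). The arithmetic is right, but those subjects are themselves responders who leave without a three-month value. The 1.6 of 20 is a base-case figure only: a 13.4-point gap is 2.7 of 20, and 25% elective stopping gives 49.4 − 31.3 = 18.1 points, or 3.6 of 20.

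Fourth, the word average in Working Study Definitions may already imply a rate, so scaling is a clarification. Primary Study Endpoints lacks that word, so it is worth stating. The safety mismatch is also milder than the efficacy one, because the analysis-set text does name major bleeding, alongside adverse drug reactions.

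**Conclusion.** The concern holds. The analysis plan's primary efficacy bullet contradicts the endpoint section in window and measure. Taken literally, it cannot be computed for subjects who leave after month 1. This rests on the text, not on the simulation.

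The size depends on assumed response, durability and stopping. In the base case the reported rate moves by up to about 8 points in the episodic cohort and under 2 in the chronic cohort. It moves more with a weaker effect or elective stopping, and far more if only continuers are counted. No data are lost and the one-month rate is recoverable. It is an important error in the primary endpoint that must be corrected and is easy to correct.

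**What to change.** In item 1 of the analysis plan, replace the efficacy bullet with the Primary Study Endpoints definition for both cohorts: at least a 50% reduction in headache days in Phase 2 against the 28-day baseline, with Phase 2 scaled to 28 logged days. Report Phase 3 as secondary and descriptive: maintenance of response among month-1 responders who continue, with the numbers eligible, continuing and logging.

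Useful in the same amendment, though not essential to the repair:

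- **Denominator.** All treated subjects, except those whose efficacy data Withdrawal of Subjects makes ineligible after consent withdrawal for reasons other than an adverse event; report their number.
- **Short logs.** Keep LOCF for two weeks or more on treatment. State in advance how subjects with less are counted, for example as non-responders, and report how many there are.
- **Safety.** Reconcile the event scope of the primary endpoint. State whether events up to 30 days after the last dose count towards it. Report events by phase with exposure, since only continuers have about three months on drug.
- **Continuation wording.** Study Design and Phase 3 require more than 50%, Study Procedures a positive response, and Appendix 1 turns on perceived benefit, while a responder needs at least 50%. These passages must be reconciled; no continuation rule is proposed here.

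The cost is a wording amendment, with no new data and no additional patients.

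### The PRU comparison uses a yes/no Responder label although headache-day change is recorded as a number, which discards about 36–60% of the outcome information (minor; cheap to improve)

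*Combined protocol and SAP*

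**What the plan says.** Under Outcomes Assessment/Statistical Analysis, item 1 (Statistical Considerations and Analysis Plan), the text begins "We will assess the number of" Responders in each study group and continues "Responsiveness will be compared with the measured PRU while on therapy". It gives no statistic, no scale and no plot. The same item calls the results descriptive only and does not expect 40 subjects (20 episodic, 20 chronic) to support statistical analysis.

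The word responsiveness has no definition of its own. Under Working Study Definitions and Primary Study Endpoints, a Responder has at least a 50% "reduction in the number of monthly headache days during the month of therapy compared with participant's own baseline"; with a smaller reduction, "she/he will be considered a Non-Responder". Item 1 restates the endpoint over a different period, but still as a yes/no cut at 50%.

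For PRU, Working Study Definitions gives a Platelet Inhibition rule ("This is a functional definition based on Platelet Reactivity"). Below 140 is positive, 141–160 "will be considered a borderline response", and above 161 negative. Nothing ties this rule to the comparison in item 1.

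The secondary efficacy endpoints include "Absolute reduction in headache days as a continuous response variable". Under Source Documents, PRU results go into the study database. No section relates the numeric headache change to PRU.

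**The concern.** The pilot is open-label and single-arm, and the Background concedes that a placebo effect could not be ruled out in the earlier clopidogrel series. The PRU comparison is the only planned analysis that sets headache outcome against measured platelet inhibition. The sponsor reasons in the same way when it explains some clopidogrel non-responders by their PRU results.

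If the outcome side is reduced to Responder or not, a subject with a 52% reduction counts the same as one who became headache-free, and a 48% reduction counts the same as none. With 40 subjects, a real gradient becomes harder to see. If most subjects respond, the Non-responder group is also small, and a chance pattern in it is easy to over-read. Leaving statistic and scale open means that both could be chosen after the data are seen.

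**Working it through.** The plan gives no power, effect size or precision for this comparison, so there is no figure of its own to reproduce.

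**Inputs from the documents.** n = 40. Guides to the response rate: over 70% in clinical use of clopidogrel, and 13/15 = 86.7% in the clopidogrel series. Both concern another drug, so a range from 50% to 87% is shown.

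**Assumptions.** Two-sided 5%; true correlation 0.3 to 0.5; bivariate normal model (step 3 changes this).

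**Step 1. Information kept by the Responder cut, with PRU fully numeric.** For a normal outcome split at response rate p, the relative efficiency is φ(z_p)² / [p(1 − p)].

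| p | φ(z_p) | Kept | Lost | Equivalent n out of 40 |
|---|---|---|---|---|
| 0.50 | 0.399 | 0.159/0.250 = 64% | 36% | 25 |
| 0.70 | 0.348 | 0.121/0.210 = 58% | 42% | 23 |
| 13/15 | 0.215 | 0.0463/0.1156 = 40% | 60% | 16 |

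**Step 2. The same loss as a chance of detection.** Simulation at n = 40 compared Spearman on full scales with a rank test of numeric PRU between Responders and Non-responders.

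| True correlation | Response rate | Full scales | Numeric PRU by Responder label |
|---|---|---|---|
| 0.3 | 70% | 43% | 27% |
| 0.4 | 70% | 69% | 46% |
| 0.4 | 87% | 69% | 32% |
| 0.5 | 70% | 89% | 67% |

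**Step 3. A different relation.** Suppose the effect is a threshold at the class cut: 80% respond if inhibited and 20% if not, with 80% of subjects inhibited. Overall response is 0.8 × 0.8 + 0.2 × 0.2 = 68%, close to the 70% above. Simulation at n = 40 gives:

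- Responder label by PRU class (Fisher): 86%
- Spearman, both on full scales: 63%
- numeric PRU by Responder label: 62%
- numeric headache-day change compared between PRU classes: 96%

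The best scale for PRU therefore depends on the shape of the relation. With PRU in classes, the numeric outcome still does better (96% against 86%). With PRU numeric, the outcome scale makes almost no difference under this model (63% against 62%).

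**Step 4. If PRU were used in classes.** The documents do not give the spread of PRU. If 95% of subjects were truly below 140, all 40 would be with probability 0.95^40 = 13%; if 98%, 0.98^40 = 45%. No class comparison would then exist.

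**The case against.** Several stronger readings are tempting, and the documents do not support them.

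- **That the plan puts PRU into three classes here.** It refers to the measured PRU, most naturally the value itself, and the class rule is a separate definition. Power figures for a Responder-by-class table, and step 4, therefore describe an analysis to which the plan does not commit.
- **That a correlation is always the more sensitive choice.** The protocol's own account is closer to a threshold: some clopidogrel non-responders had normal platelet function, and headaches stopped in four of five patients once they took prasugrel. Under such a model the class table beats Spearman (86% against 63% with 80% inhibited; 58% against 24% with 90%).
- **That a stated test is underpowered.** No test is planned. The percentages above only illustrate lost resolution. The replacement would be imprecise too: an observed correlation of 0.4 has a 95% interval of about 0.10 to 0.63 at n = 40, and −0.05 to 0.72 in a cohort of 20.
- **That the pilot fails its purpose without this analysis.** The comparison is neither a primary nor a secondary endpoint. The stated aims are feasibility, a response rate for sizing the next trial, recruitment, compliance and drop-out.
- **That the protocol expects most subjects to respond.** The 70% and 13/15 come from clopidogrel. The protocol says that no migraine patient has yet been treated with this drug and that its benefit is unknown.

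These points stand. They limit the concern to the outcome side and reduce its weight. They do not remove it: descriptive data also lose detail when a recorded number is cut in two, and the step 1 loss needs no assumption about PRU classes. Reading responsiveness as the Responder label is itself an inference, though from the preceding sentence and the only response definition given.

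**Conclusion.** The outcome half of the concern holds. Read with its own definitions, the plan compares a yes/no label with PRU although the number behind the label is collected. Under a normal model, the cut discards about 36–60% of the outcome information at response rates of 50–87%. At an assumed correlation of 0.4 and 70% response, that is about 69% against 46% chance of detection with 40 subjects. The correlation, significance level and normal model are assumptions, not figures from the plan. Keeping the outcome numeric helped clearly under the linear model, and under the threshold model when PRU was classed; in no scenario shown did it do worse with PRU on the same scale. The choice of PRU scale is a genuine trade-off, so any loss from the PRU classes is conditional. For a descriptive 40-subject pilot this is a cheap improvement of minor severity. It does not threaten the primary endpoint.

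**What to change.** In item 1 of the statistical section, replace the PRU sentence with:

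*Percent change in headache days (scaled to 28 days, treatment versus the subject's own baseline) will be shown against the on-treatment PRU value in a scatter plot marked by episodic/chronic cohort, with a Spearman correlation and 95% interval, and will also be summarised by PRU class. The Responder-by-PRU-class table will be supporting description. All of this is exploratory.*

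Scaling is needed because the treatment phase lasts 28 to 35 days and the baseline 28. The entry minimum of 6 headache days keeps the denominator of the percent change away from zero. Showing the plot and the class summary together covers both a gradient and a threshold. Before the class tables are made, values of exactly 140 and 161 must be assigned, since the current limits leave them in no class.

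The cost is one sentence and one or two more exploratory statistics. No new data, visits or subjects are needed, and the primary Responder endpoint does not change.
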